#### 8.2.3 Clinical Laboratory Assessments

Standard clinical laboratory profiles for serum chemistry, hematology, and urinalysis will be evaluated. Specific laboratory tests to be performed at each study visit are described in Section 8.1.

All clinically significant laboratory abnormalities beginning with Day 1 must be recorded as an AE in the subject's source documents and on the appropriate CRF. A clinically significant laboratory abnormality that has been verified by retesting will be followed until the abnormality returns to an acceptable level or a satisfactory explanation has been obtained.

Tests for hepatitis B surface antigen, hepatitis C virus antibodies, and HIV will be completed at screening to determine eligibility.

A UDS, an alcohol breath test, and a urine cotinine test or breath CO test will be performed at screening. An alcohol breath test and urine cotinine or breath CO test will be performed at Day -1.

# 8.2.4 Pregnancy

An FSH test will be performed at screening for all female subjects to confirm or refute postmenopausal status. A serum pregnancy test will be performed for all females at screening. Urine pregnancy tests will be performed at check-in and at follow-up for all females.

Due to teratogenic risks, all initial reports of pregnancy in female subjects or partners of male subjects must be reported to the Sponsor by the site personnel within 72 hours of their knowledge of the event.

If a female subject is suspected or known to become pregnant during the study, she should be discontinued from the study. If a female subject, or if a female partner of a male subject, becomes pregnant while enrolled in the study, information regarding the pregnancy should be submitted to the Sponsor or designee within 72 hours of the treating physician's/research personnel's awareness of the pregnancy. Every effort should be made to follow the pregnancy until completion or until pregnancy termination and, if applicable, the health of the child for 1 year post-birth.

If the outcome of the pregnancy meets the criteria for immediate classification as an SAE (ie, spontaneous abortion, stillbirth, neonatal death, or congenital anomaly [including that in an aborted fetus, stillbirth, or neonatal death]), the Investigator should follow the procedures for reporting SAEs described in Section 9.1.3.

#### 8.2.5 Electrocardiogram

A 12-lead ECG will be performed at the screening visit, Day -1, and Day 1 for subjects in Cohorts 1-3, and again at the clinic check-in (Day 9) and Day 10 for subjects in the fed cohort (Cohort 4).

#### **8.3** Pharmacokinetic Assessments

Blood samples will be collected to characterize the fasted and fed PK profiles of ISLA101, as described in Table 2.

Blood samples will be taken by fresh venipuncture or indwelling catheter; IV cannula may be utilized on days requiring intensive sampling.

The following is a listing of the PK plasma sampling times relative to the time of study drug administration, defined as the time at which the first capsule is consumed:

• At pre-dose (approximately 1 hour before study drug administration) and at 0.5, 0.75, 1, 1.5, 2, 3, 4, 5, 6, 8, 10, 12, 24, 36, 48, 72, and 96 hours after dosing.

The total amount of blood sampled from a subject will be up to approximately 185 mL during the study. This will include 72 mL (18 total blood draws × 4 mL per blood draw) for PK assessments; approximately 25 mL for screening evaluations and 12.5 mL each for other laboratory evaluations (Days -1, 1, 2, 3, and 8); and approximately 25 mL for 2 repeat lab assessments (approximately 12.5 mL each), if needed. For subjects in Cohort 4 (the food effect cohort), additional 160 mL of blood will be collected, including samples for PK assessment, laboratory evaluation (Day 9, 10, 11, 12, and 17) and repeat lab assessments.

Plasma samples will be collected and processed as per the instructions developed by the bioanalytical laboratory and aliquoted into at least 2 separate tubes. The plasma samples (split into 2 different aliquots) from each subject will be shipped in 2 separate shipments to the selected bioanalytical laboratory for analysis. The second shipment will be sent after receipt in good condition of the first shipment. The address of the selected bioanalytical laboratory will be supplied to the clinical research organization for shipment of the samples.

#### 9 ADVERSE EVENTS

The incidence and nature of any AEs, dose-limiting AEs, SAEs, vital sign changes, and laboratory abnormalities will be assessed on an ongoing basis by the SRC.

## 9.1.1 Definition of an Adverse Event

An AE is the development of an undesirable medical condition or the deterioration of a pre-existing medical condition, regardless of whether it is considered casually related to the study treatment.

The term also covers laboratory findings or results of other diagnostic procedures which are considered clinically relevant. Vital signs or laboratory abnormalities that show shifts from baseline which the Investigator considers clinically significant must be reported as AEs if they are symptomatic, require either corrective treatment or consultation, and/or lead to study drug discontinuation.

Surgical procedures themselves are not AEs; they are therapeutic measures for conditions that require surgery. The condition for which surgery is required may be an AE, if it occurs or is detected during the study period. Planned surgical measures and the condition(s) leading to these measures are not AEs, if the condition(s) was known before the subject signed the ICF. In these instances, the condition should be reported as medical history.

# 9.1.1.1 Reporting Adverse Events

All AEs, whether or not they are considered by the Investigator to be related to the study drug, must be recorded in the subject's source documents and in the electronic CRF. For each AE, the reported term, onset and end dates, severity, consequences on study drug intake (action taken), relationship to study drug, treatment provided, outcome, and information on seriousness of the event will be recorded.

The severity of the AE, relationship of the AE to study drug, and the outcome of the AE will be assessed by the Investigator.

Subjects will be monitored throughout the study for adverse reactions to the study drug and/or procedures. The subjects will be instructed to inform the study staff of any AEs that may occur at any time during the study. Observation of AEs extends from the time of ICF signing until the subject has left the study. Any AEs presenting within 30 days after the last scheduled visit will be followed up with a phone call or a visit until an outcome has been determined. After that time point, the need for additional follow-up of ongoing AEs or SAEs will be discussed between the Investigator and Sponsor.

#### 9.1.2 Treatment-Emergent Adverse Events

A TEAE is defined as any event that was not present prior to the initiation of study treatment, or any event already present which worsens either in intensity or frequency following exposure to study treatment.

## 9.1.3 Serious Adverse Events

## 9.1.3.1 Definition

A SAE is an AE occurring during any study phase that fulfils one or more of the following:

- Results in death.
- Is immediately life-threatening.
- Requires hospitalization or prolongation of existing hospitalization.
- Results in persistent or significant disability/incapacity.
- Results in a congenital anomaly/birth defect.
- Is a medically important event that may jeopardize the subject or may require medical intervention to prevent one of the outcomes listed above.

In this context, "life-threatening" means that the subject is at immediate risk of death at the time of the SAE; it does not refer to an event that hypothetically might have caused death if it was more severe. "Hospitalization" is defined as inpatient care that covers more than one calendar day. "Persistent or significant disability or incapacity" means that there is a substantial disruption of a person's ability to carry out normal life functions, compared to the person's ability prior to the study. Medical judgment should be exercised in deciding whether AEs may be considered serious because they jeopardize the subject or may require intervention to prevent one of the other outcomes listed in the definition above. The list of critical terms (1998 adaptation of World Health Organization Adverse Reaction Terminology Critical Terms List) should be used as guidance for AEs that may be considered serious because they are medically important.

## 9.1.3.2 Reporting Serious Adverse Events

All SAEs, whether or not they are deemed drug-related or expected, must be reported to the Sponsor immediately (or within 72 hours) of becoming aware of the event. The Investigator must inform the site monitor, and if required by local regulations or procedures, the Investigator should report these events to the HREC and/or national regulatory authority. The Investigator must report all SAEs on the eCRF regardless of relationship to study drug. If the site experiences a temporary disruption of the eCRF system, a back-up paper SAE report form will be available for site staff to complete.

Any SAEs should be submitted to CRO's Pharmacovigilance & Safety Services to the email listed below. CRO's Pharmacovigilance & Safety Services should be supplied with the name of the Investigator and the name, title, and contact information (email and telephone) of person submitting the report.

[contact] is the safety reporting email address for the CRO overseeing this study.

Site staff must enter the SAE information into the eCRF system as soon as the system becomes available. Should a back-up SAE form be used, the original SAE form should be kept at the study site.

Any additional follow-up including medically relevant follow-up information must be reported within the same timelines.

The SAE reports should include a detailed written report including all available data allowing the event to be documented and using only anonymized copies (with only the subject identification code: treatment number and initials) from hospitalization reports and additional examination(s). The Investigator should also report all elements concerning the follow-up of the SAE.

When reporting a death, the Investigator should supply any additional requested information such as autopsy reports (if available) and final medical reports.

The back-up SAE report form and the instructions on completion will be provided to the sites. The "Instructions for Completing the SAE Form" document provides detailed guidance on the reporting of SAEs, and AEs initially reported as non-serious which become serious.

The Sponsor will ensure compliance with all regulatory reporting requirements and notify the authorities, ethics committees, and Investigators as appropriate. All safety reporting responsibilities, timelines, and procedures will be described in detail in the Safety Management Plan.

# 9.1.4 Dose-limiting Adverse Events

Dose-limiting AEs are defined as clinically significant AEs or abnormal laboratory values that are Grade 3 or 4 in severity, based on toxicity grading scales as specified in FDA's Guidance for Industry and Investigators – Toxicity Grading Scale for Healthy Adult and Adolescent Volunteers Enrolled in Preventive Vaccine Clinical Trials.

# 9.1.5 Adverse Events of Special Interest

The following signs of drug toxicity will be deemed to be of special interest and may be dose-limiting:

- Sustained respiratory depression that results in oxygen saturation below 92%.
- Seizure
- Protracted (> 1 hour) nausea and vomiting.
- Any AE deemed by the Investigator to be dose-limiting or  $\geq$  Grade 3 in intensity.
- Clinical investigations indicating signs of drug-induced liver injury based on the following criteria from FDA guidance:

- Alanine aminotransferase (ALT) or aspartate transaminase (AST) > 8 x the upper limit of normal (ULN).
- $\circ$  ALT or AST > 5 x ULN for more than 2 weeks.
- $\circ$  ALT or AST > 3 x ULN and (total bilirubin > 2 x ULN or international normalized ratio > 1.5).
- ALT or AST > 3 x ULN with the appearance of fatigue, nausea, vomiting, right upper quadrant pain or tenderness, fever, rash, and/or eosinophilia (> 5%).
- Any clinically significant findings of blood chemistry and hematology.

Depending on the severity of these and/or other AEs or the occurrence of more than 1 AE in the same subject, the subject(s) may be unblinded if it is deemed necessary for the treatment of AEs.

## 9.1.6 Severity

The severity (intensity) of each AE must be assessed according to the following classification:

- Mild: does not interfere with routine activities.
- Moderate: interferes with routine activities.
- Severe: subject is unable to perform routine activities.

## 9.1.7 Relationship

The relationship of any AE to the study drug must be assessed, according to the following rating, by the clinician who examines and evaluates the subject based on temporal relationship and clinical judgment:

- Definitely: The AE is clearly related to the study drug.
- Probably: The AE is likely related to the study drug.
- Possibly: The AE may be related to study drug.
- Unlikely: The AE is doubtfully related to study drug.
- Unrelated: The AE is clearly not related to the study drug.

#### *9.1.8 Outcome*

The outcome of each AE may be classified as resolved (spontaneously or with treatment) or unresolved.

Any subject who experiences an AE (whether serious or non-serious) or has a clinically significant abnormal laboratory test values will be evaluated by the Investigator or a monitoring physician and will be treated and/or followed up until the symptoms or values return to normal, or acceptable levels, as judged by the Investigator. Where appropriate, medical tests and/or examination) will be performed to document resolution of events.

# 9.1.9 Expectedness

An unexpected adverse reaction is any untoward and unintended response that is related to the administration of the study drug at any dose that is not consistent with the applicable product information (as described in the Investigator's Brochure for ISLA101).

All suspected unexpected serious adverse reactions (SUSARs) will be the subject of expedited reporting. The Sponsor and/or CRO shall ensure that all relevant information about a SUSAR that is fatal or life-threatening is reported to the relevant competent authorities and HREC within 7 days after the Sponsor becomes aware of the event. Relevant follow-up information will subsequently be communicated within an additional 8 days. All other SUSARs will be reported to the relevant competent authorities and HREC within 15 days after the Sponsor becomes aware of the event. All Investigators should follow SUSARs until the event is resolved or until, in the opinion of the Investigator, the event is stabilized or determined to be chronic. Suspected unexpected serious adverse reactions that occur after the subject has withdrawn from the clinical study must be reported by the Investigator to the Sponsor.

#### 10 PLANNED STATISTICAL METHODS

## **10.1** General Considerations

A statistical analysis plan (SAP) describing all statistical analyses will be provided as a separate document prior to data lock-out.

Descriptive statistics will be used to provide an overview of the safety results. For categorical parameters, the number and percentage of subjects will be presented. For continuous parameters, descriptive statistics will include n (number of subjects), mean, standard deviation, median, minimum, and maximum. No imputations will be made for missing data.

A brief outline of planned statistical analyses is presented below.

## 10.2 Determination of Sample Size

No formal sample size calculation was performed. The study is considered exploratory with a sample size of 8 subjects per cohort (2 placebo + 6 active). This cohort size and active/placebo ratio are considered standard to evaluate safety profile and to provide sufficient PK information for future development of the compound.

## 10.3 Analysis Populations

In fasted and fed cohorts, 2 analysis populations will be used to summarize the results from this study:

Safety Population: All subjects who receive at least 1 dose of study drug (active and placebo). Safety analyses will be based on the safety population.

**PK Population:** All subjects in the Safety Population who have a pre-dose PK sample and at least 1 post-dose analyzable PK sample.

Subjects who received planned doses of ISLA101 will be included in the PK evaluation and statistical comparisons, based on availability of sufficient PK profiles. Actual treatments will be used for all analyses.

All subjects who receive at least one dose of the study drug (placebo or active) will be included in the safety analyses.

# 10.4 Disposition and Demographics

Subject disposition will be summarized and will include all subjects who have received one dose of study drug in the safety population, subjects in the PK population, and number and percent of subjects who complete or prematurely discontinue from the study along with reason for discontinuation. Demographic data will be summarized using descriptive statistics for all subjects who were randomized in this study and took at least 1 dose of study drug.

## 10.5 Safety Analysis

All safety data from the study will be listed by subject, dose, and cohort. Changes in safety assessments from screening to post-dose measurements will be assessed using summary statistics (mean, minimum, maximum, standard deviation, and corresponding sample size [N] for continuous variables, and frequency of category shifts from screening to post-study for discrete variables) for each part/cohort. Additionally, summary statistics for vital signs (blood pressure, pulse, pulse oximetry, and respiratory rate) and oral temperature will be reported.

Adverse events will be coded using the toxicity grading scale tables as specified in Guidance for Industry and Investigators – Toxicity Grading Scale for Healthy Adult and Adolescent Volunteers Enrolled in Preventive Vaccine Clinical Trials and Medical Dictionary for Regulatory Activities terminology. The AEs will be summarized by dose and visit and overall. The AEs will be tabulated and summarized by body system, preferred term, severity, frequency, and relationship to study drug. A listing of SAEs will be provided.

Change from screening in clinical laboratory parameters and vital sign parameters will be summarized by visit and overall. Shift tables for key safety parameters including clinical lab investigations will be presented. Frequency descriptors for the safety analyses will be reported as needed.

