# Safety and This study will assess the safety and tolerability of the chosen doses of ISLA101 **Tolerability** (fenretinide oral capsules) as assessed by AEs, TEAEs, vital signs, physical **Evaluation** examinations, and clinical laboratory tests. As clinical studies from IND38892 and from the published literature showed ocular toxicity upon treatment with fenretinide (eye irritation, dryness of eyes, nyctalopia), an ophthalmologist will be available to evaluate all significant ocular complaints. Discontinuation from the study will be at the discretion of the ophthalmologist. Due to teratogenic risks, all initial reports of pregnancy in female subjects or partners of male subjects must be reported to the Sponsor by the site personnel within 72 hours of their knowledge of the event. The safety and tolerability data will be reviewed by an independent SRC before proceeding to the next dose cohort. **Dose-limiting Adverse** The incidence and nature of any AEs, dose-limiting AE, SAEs, vital sign changes, **Events** ECG changes, and laboratory abnormalities will be assessed on an ongoing basis by the Investigator. Dose-limiting AEs are defined as clinically significant AEs or abnormal laboratory values that are Grade 3 or 4, based on toxicity grading scales as specified in FDA's Guidance for Industry and Investigators – Toxicity Grading Scale for Healthy Adult and Adolescent Volunteers Enrolled in Preventive Vaccine Clinical Trials. The following signs of drug toxicity will be deemed to be of special interest: • sustained respiratory depression that results in oxygen saturation below 92% seizure • protracted nausea and vomiting • any AE deemed by the Investigator to be dose-limiting or Grade 3 and above • signs of drug-induced liver injury based on the following criteria from FDA guidance (Drug-Induced Liver Injury: Premarketing Clinical Evaluation): ALT or AST $> 8 \times ULN$ • ALT or AST > 3 x ULN and (total bilirubin > 2 x ULN or international normalized ratio > 1.5) • ALT or AST > 3 x ULN with the appearance of fatigue, nausea, vomiting, right upper quadrant pain or tenderness, fever, rash, and/or eosinophilia (> 5%) Escalation from one dose level to the next will occur following the safety review by the SRC. If blinded study drug demonstrates an acceptable safety profile in the previous cohort, enrollment of the next higher dose cohort may begin. In the case of dose-limiting AE, dose reduction or repeat of the cohort with the previously tested dose may occur. **Dose Escalation** The decision to enroll the sequential cohort at the next dose level will be based on Criteria the safety data from previous dose cohorts. Dose escalation will depend on the emergence of dose-limiting AEs and review of the safety data. Progression to the next higher dose will only occur if the previous dose level was deemed to be safe and well tolerated by the SRC. Safety data sets to be reviewed by the SRC for dose escalation determination will include all available data up to 96 hours post-dosing for subjects enrolled into each dose-level cohort. A minimum of 7 subjects' data will be evaluated to make dose escalation decisions.

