# SCHEDULE OF ASSESSMENTS

Table 1

Study Procedures and Assessments to Dose Under Fasted (Cohorts 1-3) and Fed Condition (Cohort 4)

				Cohorts 1-3	s 1-3							Cohort 4	4		
	Study Period	Screening	Clinic Check- in	Tra	eatme	Treatment Period	iod	Follow- up/ET	Clinic Check- in	·	Treatment Period	nent P	eriod		Follow- up/ET
Study Procedure	Study Day	-28 to -2	-1	1	2 3	3 4	5	8	66	10	11	12	13	14	17
	Visit Window (days)	N/A		eduI	Inpatient			+/-1	£-/+		Ir	Inpatient	t.		+/-1
Informed Consent		X							X						
Inclusion/Exclusion Criteria		X	X						X						
Demographics		X													
Height and weight		X							X						
Medical History		X	X						X						
Vital Signs 		X	X	X	X	X	X	X	X	X	X	X	X	X	X
12-lead		;	;	;					;	;					
electrocardiogram (ECG) 		×	×	×					×	×					
Full Physical Exam		X	X					X	X						X
Hep B, Hep C, HIV		X													
Safety laboratory tests															
(chemistry,		X	×	×	×	×	×	×	×	×	×	×	×	×	×
coagulation, urinalysis)															
Pregnancy test 		X	X					X	X						X
FSH 		X													
Urine screen for drugs of abuse 		X							X						
Alcohol breath test		X	X						X						
Admission			X	$\exists$	$\dashv$				X						

Study drug administration			×						X 6					
High-fat, high-calorie breakfast									X					
PK blood samples 			X		X	X			X	X	X	X	X	
Adverse events 	X	X	X	X	X		X	X	X	X	X	X	X	X
Concomitant medication review	X	X	X	X	X	X	X	X	X	X	X	X	X	X
Discharge						X							X	

ECG = electrocardiogram; ET = early termination; FSH = follicle-stimulating hormone; Hep = hepatitis; HIV = human immunodeficiency virus; PK = pharmacokinetic(s);

Vital signs include blood pressure, pulse, respiration and temperature.

12-lead ECG will be performed in triplicate at screening, and on Day -1 (check-in) to confirm eligibility, and on Day 1 at 5 hours (±15-minute) post dose. A single ECG will be performed on Day 9 (check-in) and on Day 10 at 5 hours (±15-minute) post dose.

A serum pregnancy test will be performed at screening and urine pregnancy test will be performed at check-in and at follow-up for all female subjects.

4 For all female subjects to confirm or refute postmenopausal status.

A nicotine urine or breath test may be utilized for tobacco use testing at site discretion.

Study drug will be administered approximately 30 minutes after start of a high-fat, high-calorie meal; 100% meal consumption is preferred.

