#### 5.3 Stopping/Halting Rules

Further enrollment and study drug administration will be stopped if any of the following events occur:

- A single SAE regardless of organ system if it is possibly, probably, or definitely related to the study drug.
- Grade 3 or higher AEs and laboratory abnormalities determined to be possibly, probably, or definitely related to study drug.
- Death of any subject considered related to study drug unless the SRC determines it is unrelated to study drug.
- An anaphylactic reaction to study drug in any subject.
- A potentially life-threatening AE or SAE, unless the SRC determines it is unrelated to study drug.
- A pattern of significant symptoms, physical findings, or laboratory abnormalities that, although individually minor, collectively may represent a safety concern in the opinion of the Investigator or the medical monitor and are judged by the SRC to be at least possibly related to study drug.
- Sponsor's decision to terminate the study for any reason.

Dose-limiting AEs that will halt further enrollment into the affected cohort and study drug administration within the cohort are described in Section 9.1.4. Additionally, if any AEs of special interest (see Section 9.1.5) occur that meet the following criteria, they will be considered dose-limiting:

- Any two ≥ Grade 2 AE of special interest, unless they are clearly and incontrovertibly due to extraneous causes.
- Any one ≥ Grade 3 AE of special interest, unless the event is clearly and incontrovertibly due to extraneous causes.
- Any SAE of special interest, unless the event is clearly and incontrovertibly due to extraneous causes.

The HREC and the FDA will be notified if the study hold criteria are met.

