## 8.1.1 Screening (Days-28 to Day -2)

Prior to any study procedure, the subject will read and sign an ICF. All subjects will receive a copy of the signed ICF. The informed consent process will be noted in the subject's medical record.

Within approximately 28 days of the study drug administration, the screening visit should be completed. All subjects will be evaluated for adherence with study inclusion/exclusion criteria. A complete medical history evaluation, including surgical history and demographic data (age, gender, ethnicity, and race) will be completed for each subject. A complete history of all medications taken within 4 weeks of this visit will be obtained. Subjects will be instructed about permitted therapies and study restrictions (see Section 7).

A full physical examination will be performed. Vital signs will be measured (blood pressure, pulse, respirations). Temperature will be measured. Clinical significance will be noted for any abnormal findings. A serum pregnancy test will be done on all female subjects. Follicle-stimulating hormone (FSH) will be measured to confirm postmenopausal status. A urine drug screen will be done on all screening subjects. A breath alcohol test will be administered. Body mass index (BMI) will be determined from height and weight (shoes off) measurements. BMI can be calculated using pounds and inches, or kilograms and centimeters, with the following equations:

- BMI = [Weight in Pounds/ (Height in Inches x Height in Inches)] x 703
- BMI = Weight in Kilograms/ (Height in centimeters x Height in centimeters)

For any out-of-normal range values, clinical significance will be noted. The clinical laboratory tests include:

- Serum Chemistry: alanine transaminase, albumin, alkaline phosphatase, aspartate
  transaminase, blood urea nitrogen, calcium, carbon dioxide, chloride, creatinine, glucose,
  inorganic phosphorus, magnesium, potassium, sodium, total bilirubin, total protein, uric
  acid.
- Hematology: differential white blood cell count, hematocrit, hemoglobin, platelet count, red blood cell count, international normalized ratio (INR).
- Serology: hepatitis B surface antigen, hepatitis C antibody titer, HIV.
- Serum Pregnancy Test: hCG will be conducted for all female subjects.
- FSH will be tested for all female subjects to confirm or refute postmenopausal status.

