## 8.2.1 Vital Signs

Vital signs will consist of respiratory rate, heart rate, and semi-recumbent blood pressure. Subjects should be resting in a semi-recumbent position for at least 3 minutes prior to and during vital signs measurement. When the time of vital signs measurement coincides with a blood draw, the vital signs will be taken before the scheduled blood draw where possible while ensuring the blood draw is within the window specified in the protocol. Additional vital signs may be performed at other times if deemed necessary.

If temperature measurement is oral, subjects should not eat or drink hot or cold foods or beverages within 15 minutes of oral temperature measures. On dosing days, temperature will be taken prior to dosing.

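### Protocol 10.5 calls for pulse-oximetry summary statistics and 9.1.5 uses a 92% saturation threshold, but no vital-signs schedule, parameter list or shell includes saturation (minor)

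*Protocol*

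**What the plan says.** Saturation or oximetry appears in three places, all in the protocol.

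- Section 10.5 (Safety Analysis) says that "summary statistics for vital signs (blood pressure, pulse, pulse oximetry, and respiratory rate) and oral temperature will be reported". It also plans summaries by visit of change from screening in vital-sign parameters.
- Section 9.1.5 lists among the events of special interest "Sustained respiratory depression that results in oxygen saturation below 92" per cent. The synopsis row on dose-limiting adverse events has the same criterion.

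Section 5.3 links that list to cohort halting: "Additionally, if any AEs of special interest (see Section 9.1.5) occur that meet the following criteria, they will be considered dose-limiting". The criteria that follow are two events of Grade 2 or higher, one of Grade 3 or higher, or any serious event, unless clearly due to other causes.

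The operational text defines vital signs without saturation. The Table 1 footnote reads "Vital signs include blood pressure, pulse, respiration and temperature". Section 8.2.1 reads "Vital signs will consist of respiratory rate, heart rate, and semi-recumbent blood pressure" and deals with temperature separately. It then leaves room for extra readings: "Additional vital signs may be performed at other times if deemed necessary".

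The SAP follows the operational text. Section 4.1.4 gives the parameters recorded on the vital-signs eCRF page, and section 6.8.4 limits the vital-signs analysis to that list.

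**The concern.** A summary that the protocol says will be reported has no planned measurement behind it. An investigator who follows Table 1 and section 8.2.1 exactly will have no saturation data to summarize. Ad hoc readings do not help, because SAP 5.1.5 admits only values from scheduled visits or time points to summary tables.

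The same omission touches a safety criterion. One element of a special-interest event, which can become dose-limiting under 5.3, can be checked only if someone decides at the time to take a reading. The safety review committee escalates on data up to 96 hours after dosing, and no saturation value is scheduled to be among those data.

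**Working it through.** The plan gives no figure to reproduce. The check is a comparison of texts, followed by two counts.

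**Where saturation appears and where it does not**

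| Place | Content | Saturation |
|---|---|---|
| Protocol synopsis, dose-limiting AEs | special-interest criterion | yes |
| Protocol 9.1.5 | special-interest criterion | yes |
| Protocol 10.5 | summary statistics | yes |
| Protocol Table 1, footnote 1 | blood pressure, pulse, respiration, temperature | no |
| Protocol 8.1.1 | blood pressure, pulse, respirations; temperature | no |
| Protocol 8.2.1 | respiratory rate, heart rate, blood pressure; temperature | no |
| SAP Table 1, footnote 1 | same as the protocol footnote | no |
| SAP 4.1.4 | SBP, DBP, pulse, respiratory rate, temperature, height, weight, BMI, BSA | no |
| Shell for Table 14.3.5.1 | SBP, DBP, pulse, respiratory rate, temperature, BSA | no |
| Shell for Listing 16.2.9.1 | same parameters as SAP 4.1.4 | no |

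Three places use saturation, and none of the seven that list vital-sign components includes it. The shell for Table 14.3.5.2 gives no parameter order of its own, but SAP 6.8.4 ties it to the 4.1.4 list. Section 10.5 names five measures: blood pressure, pulse, pulse oximetry, respiratory rate and oral temperature. SAP 4.1.4 carries four of the five.

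**Planned subject-visits with vital signs (Protocol 8.1 to 8.1.4)**

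- Fasted: screening, Day -1, Days 1 to 5 and Day 8 make 1 + 1 + 5 + 1 = 8 visits; 24 subjects × 8 = 192.
- Fed: Days 9 to 14 and Day 17 make 6 + 1 = 7 visits; 8 subjects × 7 = 56.
- Total: 192 + 56 = 248, with no scheduled saturation reading.

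This count assumes one set of vital signs per visit. Note b to the PK sampling table (Protocol Table 2, SAP Table 3) says that vital signs come before PK samples. If that means a set before every draw, the PK-linked sets alone number 18 draws × (24 + 8) dosing occasions = 576. The text does not settle which is meant.

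**What happens to an ad hoc reading**

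Under SAP 6.8.4 it would be listed if entered in the database. Under SAP 5.1.5 it would not enter Table 14.3.5.1 or 14.3.5.2.

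**Which events depend on the saturation element**

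- Grade 3 or higher: of special interest under 9.1.5 whatever the saturation. If related to study drug, it also stops the study under 5.3.
- Serious and related, or potentially life-threatening: stops the study under 5.3, in the second case unless judged unrelated.
- Any event that the investigator deems dose-limiting: of special interest under 9.1.5 whatever the saturation.
- What remains is a non-serious Grade 2 respiratory event that the investigator does not deem dose-limiting. Under 5.3 it counts only as one of two special-interest events of Grade 2 or higher.

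**The case against.** The strongest reply is that this is one stray phrase. Protocol 10.1 calls Section 10 a brief outline and leaves the full analysis to the SAP. The SAP text and shells agree with one another and with the protocol's own definition of vital signs. Pulse oximetry is not named among the primary endpoints. The documents report no respiratory signal for oral fenretinide: the common events in Protocol 1.2.1 are headache, diarrhea, nausea, skin irritation and nyctalopia, with no serious events. The criterion starts from a clinical sign, subjects are confined to Day 5, and Protocol 8.1.5, 8.2 and 8.2.1 allow extra measurements. The adverse-event listings have columns for special-interest events and signs of drug toxicity.

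Most of this stands and limits the weight of the point. It does not remove the conflict. An outline may omit detail, but this one names a measure and says that it will be reported, and the measure is absent from the same protocol's schedule. Discretionary readings can confirm an event; they cannot supply a summary by visit.

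A reader might infer three stronger claims, which the documents do not support.

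- *That the 92% criterion cannot be applied without a pre-dose value.* The threshold is absolute. A baseline would matter only for a change summary.
- *That serious respiratory depression would escape the halting rules.* Section 5.3 acts on grade and seriousness, and the other routes set out above catch such events.
- *That SAP 7.1 is wrong to declare no changes from the protocol.* The SAP is based on a protocol version dated 18 October 2023, and the protocol supplied is dated 20 November 2023. The earlier text is not available, so nothing can be said about 7.1.

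**Conclusion.** The inconsistency is real and lies within the protocol itself, so it does not depend on which version the SAP followed. As written, the pulse-oximetry summary in 10.5 cannot be produced, and the saturation element of the special-interest criterion rests on discretionary readings alone. Two tables and one listing are affected.

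Severity is minor. The count of 248 shows how far the omission reaches; it does not measure harm. The documents give no desaturation rate for fenretinide, so no number of missed events can be estimated. The conclusion assumes that SAP 4.1.4 fully describes the vital-signs eCRF page and that no site procedure outside these documents schedules oximetry. The visit count also assumes that all eight subjects return for Cohort 4.

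**What to change.** **Preferred.** Add SpO2 to the existing scheduled vital-sign assessments: the Table 1 footnotes in both documents, Protocol 8.1.1 and 8.2.1, SAP 4.1.4, Tables 14.3.5.1 and 14.3.5.2, and Listing 16.2.9.1. When a value is below 92%, require a repeat at a stated interval, so that whether the fall is sustained can be judged. Record repeats as unscheduled, so that they appear in the listing and stay out of the summary tables.

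**Minimum.** Delete pulse oximetry from Protocol 10.5, and require an SpO2 reading whenever respiratory depression is suspected. This removes the conflict and gives the criterion a defined source, but the summary is given up.

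**Cost of the preferred change.** One non-invasive reading per set of vital signs, one eCRF field and an occasional repeat. That is about 248 readings at one set per visit. It is more if note b means a set before each PK draw, with up to 576 PK-linked sets; the sponsor should settle that reading at the same time. No extra visit or blood draw is needed.
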